### 3. Method

#### 3.1 Recruitment

##### 3.1.1 Initial Contact

Older adult participants will be recruited through the PREVENT-AD cohort as an optional sub-study, by reaching out to potentially eligible participants by phone and email. Screening procedures will involve verbally screening potential participants over the phone. A staff member doing the screening will begin with an overview of the HABS project. The screener will then obtain verbal consent (see telephone script). The telephone script will ask questions concerning inclusion and exclusion criteria. The total time to administer all screening questions is approximately 40 minutes. The telephone screen will also assess the level of physical activity via self-reported physical activity. If eligibility is verified, a date and time will be scheduled for a virtual meeting between the participant and a researcher where the formal study consent will be signed. Those individuals that are deemed ineligible from the screening call will have their forms kept in a separate file on REDCap. This information will be used to quantify how many were ineligible from the screening call and the reasons for ineligibility.

The criteria will be assessed by one of the listed study personnel. No special expertise is required to evaluate screening responses. If a participant requires exclusion due to information received during a session, they will be contacted via telephone or email and informed that they have been excluded from further study, nevertheless remaining part of the PREVENT-AD cohort. The reason provided for their exclusion will be brief and will include a statement such as, "Based on the data collected in your last session, we will not require any further testing. As indicated in the beginning, participation depends on several factors and not all participants qualify for the entire study."

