### 5.5 Neuropsychological Assessment

If participants pass this second screening, they will complete neuropsychological and behavioural inventories. We expect testing to take about 3 hours and will administer the assessments with breaks every ~40 minutes to reduce fatigue. They will complete behavioural inventories that capture individual differences in traits potentially predicting responsiveness to the intervention. These measures (listed in the attached spreadsheet) include validated questionnaires to assess factors like motivation for physical activity, self-efficacy for exercise, self-efficacy for walking, barriers to exercise, mood, conscientiousness and grit, growth mindset, loneliness, future time perspective, and purpose in life. Participants' educational attainment and total personal income levels will also be collected to create a measure of socioeconomic status, as described by [Hartanto et al. \(2019\)](#) [19]. These questionnaires will be administered through REDCap, a "secure, HIPAA-compliant, web-based application... housed in a secure local data center, behind the Tufts Medical Center firewall, and all web-based information is encrypted" ([tuftsctsi.org/research-services/informatics/redcap-research-electronic-data-capture/](http://tuftsctsi.org/research-services/informatics/redcap-research-electronic-data-capture/)).

Participants will also complete a cognitive battery (also listed in the attached spreadsheet) that examines important cognitive constructs that have been associated with changes in physical activity and aging including executive function (i.e., the Brief Test of Adult Cognition by Telephone [BTACT]), working memory (n-back, WAIS-IV Digit Span Forwards and Backwards), sustained attention and motor speed (WAIS-IV Coding test, simple reaction time), verbal fluency (Category and Phonemic Fluency tests), and episodic memory (Hopkins Verbal Learning Test – Revised (HVLT-R). Neuropsychological measures will be administered remotely via telephone encrypted videoconferencing (using HIPAA compliant Zoom software) and secure, coded platforms such as Test My Brain ([testmybrain.org](http://testmybrain.org)). Additional paradigms are described below:

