After compiling all data across the 3 different data servers, data will be checked for completeness and correctness using frequency distributions (for missing data and out-of-range A-B values). Group differences at baseline are examined for variables including demographic factors (i.e., age, sex, educational level, socioeconomic status, culture), baseline sedentary time, self-report sitting time, and estimated fitness, in order to detect potential confounding factors. For the primary hypothesis that social motivation + self-transcendence messages decrease sedentary time more than an active control, all outcome measures about sedentary behaviour are first quantified using available software. Changes in sedentary behaviour (% daily sitting and lying time, minutes/per day in physical activity, count of steps) over time (3-time points) are analyzed using linear mixed effect models to account for the correlated data and likely heterogeneous variability.

Non-linear changes across 3-time points are also examined by including quadratic effects. These models will include a random intercept and slope to account for subject-specific changes as well as a group (2) x time (3) interaction fixed effect. This allows for modelling of the effect of our intervention as a function of both groups and time as well as accounting for potentially confounding covariates. All model assumptions will be tested both visually and formally and associations between covariates will be assessed to protect against multicollinearity.

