Analyses on the resting state and task-based fMRI analyses are considered secondary. Briefly they will be modeled using the general linear model approach. First-level analyses will include all necessary nuisance regressors to minimize motion artifacts influence, spatial smoothing kernel and high pass filtering, as well as physiological aliasing for the low-frequency fluctuations in resting state data. To answer questions about the intervention effect and prediction of behavioural change, both a priori ROI seed-based analyses of functional connectivity are performed as well as data-driven whole-brain multi-voxel pattern analysis, modularity analyses and graph theory per several previous publications using data-driven approaches to predict clinical outcomes. Besides the primary outcomes, adherence and drop-outs are also included in the prediction model as outcome variables, to examine what individual characteristics affect participation in the current intervention. Robust-prediction models of MRI data and psychosocial measures will be generated using cross-validation methods to improve the generalization of the results.

Selection bias will also be considered in our study by comparing characteristics between the source population (i.e., PREVENT-AD participants) and the study sample. For eligible participants invited to participate in the study, we will document the proportion of those who decline and agree to participate. We will compare demographic information (age, sex, education, ethnicity, socioeconomic status, smoking status, and self-reported physical activity) between those who agree and those who refuse to participate using t-tests and chi-square tests of independence. Multivariate logistic regression models will be used to determine whether these characteristics are associated with acceptance relative to refusal to participate in the study.

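### The acceptance model lists education beside a socioeconomic score built from education, so if both enter one model the adjusted education odds ratio can be null or wrongly signed when income also matters

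*Protocol*

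**What the plan says.** Protocol section 6b, in its paragraph on selection bias, sets out a comparison of "age, sex, education, ethnicity, socioeconomic status, smoking status, and self-reported physical activity) between those who agree and those who refuse". Education and SES appear there as two separate characteristics. They are first compared between "those who refuse to participate using t-tests and chi-square tests of independence". The plan then adds an adjusted analysis: "Multivariate logistic regression models will be used to determine whether these characteristics are associated with acceptance relative to refusal to participate".

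Section 5.5 describes the only SES measure in either document: "educational attainment and total personal income levels will also be collected to create a measure of socioeconomic status". It gives no weights and points to a cited paper for the construction. Nothing in section 6b drops education when SES is entered, or puts income in place of the score.

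One sentence elsewhere in section 6b could be taken as a safeguard: "associations between covariates will be assessed to protect against multicollinearity". It closes the description of the linear mixed models for the activity outcomes.

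**The concern.** A composite and one of its own components are both listed as predictors, and here the coefficients are themselves the result. The stated question is whether each characteristic is associated with acceptance. Holding the composite fixed while education rises forces income to fall, so the education coefficient describes a trade of income for education and not the effect of education. The SES coefficient in turn carries only the income effect.

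At stake is how one adjusted odds ratio is read. The report could say that better-educated people tend to refuse when they do not. It could also say that education is unrelated to acceptance after adjustment when it is related. The unadjusted and adjusted education results could point in opposite directions, and many readers would trust the adjusted one.

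**Working it through.** The documents give no figure for this analysis, so there is nothing to reproduce.

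**Inputs from the documents.** SES is made from education and personal income (protocol section 5.5). Education and SES are both candidate predictors of acceptance (section 6b).

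**Assumptions, not in the documents.** E and I are standardised education and income, with correlation ρ of 0.2 to 0.6. SES = wE + (1−w)I, with w from 0.3 to 0.7. ORs per standard deviation run from 1.0 to 2.0. About half of those invited accept.

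**Algebra.** Let the true log-odds of acceptance be aE + cI. Since I = (SES − wE)/(1−w),

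aE + cI = [a − c·w/(1−w)]·E + [c/(1−w)]·SES.

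At w = 0.5 the education coefficient is a − c.

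**Numbers put in** (ln 1.2 = 0.182, ln 1.5 = 0.405, ln 2 = 0.693):

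| True education OR | True income OR | w | Education coefficient beside SES | Fitted education OR |
|---|---|---|---|---|
| 1.5 | 1.0 | 0.5 | 0.405 − 0 = 0.405 | 1.50 |
| 1.5 | 1.2 | 0.5 | 0.405 − 0.182 = 0.223 | 1.25 |
| 1.5 | 1.5 | 0.5 | 0.405 − 0.405 = 0 | 1.00 |
| 1.5 | 2.0 | 0.5 | 0.405 − 0.693 = −0.288 | 0.75 |
| 1.0 | 1.5 | 0.5 | 0 − 0.405 = −0.405 | 0.67 |
| 1.5 | 1.5 | 0.3 | 0.405 − 0.405 × 0.429 = 0.232 | 1.26 |
| 1.5 | 1.5 | 0.7 | 0.405 − 0.405 × 2.333 = −0.541 | 0.58 |

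Logistic fits to 400,000 simulated people agree with every row to within 0.02. With education and income as separate terms, the fits recover the true education OR in every scenario (1.49 to 1.51 for a true 1.50).

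**Direction against the unadjusted result.** With ρ = 0.4, no education effect and an income OR of 1.5, education alone gives 1.17, education beside SES gives 0.67, and education beside income gives 1.00.

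**At a plausible study size.** For 240 invited, ρ = 0.4, equal weights and a true education OR of 1.5:

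- Income OR 1.5: education reaches p<0.05 in 5% of runs beside SES, against 77% beside income.
- Income OR 2.0: 21% against 74%, and the fitted sign is negative in 86% of runs beside SES.
- Income OR 1.2: 15% against 77%, with a negative sign in 18%.

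For 120 to 240 invited, with income alone acting (log-odds 0.5 per standard deviation), the fitted education OR is about 0.60. It reaches p<0.05 in 29 to 53% of runs, against 4 to 6% with separate terms.

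**Would a collinearity check catch it?** At equal weights the variance inflation factor of education beside SES is 2/(1−ρ): 2.5, 3.3 and 5.0 at ρ = 0.2, 0.4 and 0.6. The usual cut-offs of 5 or 10 would often pass it. Such a check also looks at precision, and does not restore the meaning of the coefficient.

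**The case against.** The strongest reply is that the plan already answers the education question elsewhere. The unadjusted tests compare education without SES. Under the assumptions above, with education mattering alone (log-odds 0.5) or together with income (0.4 each), they detect the gradient in about 73 to 98% of runs with 120 to 240 invited. This stands. A reader might infer that the plan would miss a real education gradient, or that this model is the plan's sole check on selection. Neither is supported: the same paragraph also plans the proportions who agree and decline, and a comparison of the source cohort with the study sample.

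It can also be said that the weights are unknown and that the plural, models, may mean separate fits. Both are fair. Education minus income is exact only for an equally weighted score of standardised components. One joint model is the natural reading of section 6b, but not the only possible one.

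Third, section 5.5 places the inventories after consent: "If participants pass this second screening, they will complete neuropsychological and behavioural inventories". SES for people who refuse may therefore come from another source, and a cohort measure not built from education would remove the overlap. No such measure is described, so the point stands on what is written. Where refusers' SES comes from is a missing detail, not a demonstrated bias.

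A reader might go further and infer that refusers also lack self-reported activity. The documents do not support that for the population named. Section 6b concerns eligible invitees, and section 3.1.1 verifies eligibility on a call in which "The telephone screen will also assess the level of physical activity via self-reported physical activity". Nor do they support widening the denominator to every cohort member contacted, which would mix ineligibility with refusal.

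**Conclusion.** The concern holds in a limited form. If education and the SES score of section 5.5 enter one logistic model, the adjusted education OR does not measure the education effect, and the SES OR carries only the income effect. The education OR may be attenuated, null or reversed, depending on the income effect and on the weight. With both true ORs at 1.5, the fitted value runs from 1.26 down to 0.58 as education's weight goes from 0.3 to 0.7. With no income effect there is no bias, only lost precision. These sizes rest on the assumed weights, correlation, effects and numbers invited, none of which the documents give. The form of the distortion rests only on the score being a weighted sum that contains education.

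The consequence is confined to a supporting, descriptive analysis. The treatment comparison is untouched: the SAP's covariates for Aim 1 include SES but not education, and are declared of no interest in themselves. Section 6b also names education and SES together for the imaging models, but there they are nuisance terms whose coefficients are not interpreted. The point is worth correcting because the correction is nearly free.

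**What to change.** In the selection-bias paragraph of section 6b, state that education will not be entered in the same model as a composite that contains it. If income is available for both those who agree and those who refuse, enter education and income as separate terms and leave the composite out. If it is not, enter either education or SES, and name which in advance. No document shows that the cohort record holds income, so this needs checking before the first option is chosen.

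The cost is a sentence or two in section 6b and no new data collection. The downside is that, with only one of the terms in the model, the effects of education and income on acceptance are not separated, and the report should say so. The unadjusted comparisons and the population in section 6b can stay as they are.

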## 7. Data confidentiality and protection

To reduce the risk of breach of confidentiality we will separate all information obtained during the screening period from identifying documents. All research data will be anonymized. These documents will be stored in a separate location from the data and the screening information on REDCap, in a project file to which only lab personnel have access. Data that is saved electronically (computer system) is protected by the REDCap firewalls. During data collection from participants, staff will converse with participants and have knowledge of names, but will be encouraged to maintain a first-name basis whenever possible. All data will be blinded and only used in aggregate to understand physical activity effects on the brain and cognition.

We will ensure participant confidentiality by using PREVENT-AD's coding for all participants' data according to their numbering system and separating it from the informed consent. All informed consent documents and data files pertaining to subject data information will be kept in encrypted, password-protected files on an encrypted, password-protected flash drive that only researchers involved in the project will have access to. Multiple levels of password protection (e.g., record, file, directory, server, and computer levels) are employed to ensure data security. All personnel involved in the study will be approved through the IRB and agree to protect the security and confidentiality of identifiable information. All data pertaining to the individual will be stripped of all identifying information. Paper copies of data will be destroyed 7 years from the date of study completion. Trial results will be uploaded to *Clinicaltrials.gov* in compliance with the NIH standards of reporting.

## **8. Incidental findings**

If any study results are revealing a direct implication of the health and safety of the participant (i.e. requiring immediate medical intervention or in the near future), the incidental findings will be transmitted to the physician of the participant indicated on the informed consent form. In cases where the physician is not reachable or not indicated on the informed consent form, the clinical staff of the Douglas Hospital will inform the participant as soon as possible. This procedure will be followed for all participants whether or not they wish to be contacted for less serious incidental findings.

## **9. Risks**

The procedures, techniques, equipment, and measures to be used in the proposed study are commonly used in educational and research settings involving human subjects, and are not new, untested, or of questionable safety. Experimenters are aware of the potential for serious adverse events to occur with any type of moderate-intensity exercise, but such risks are considered minimal in this population. In addition, the primary focus of this study is the decrease in sedentary behavior and an increase in walking rather than moderate to vigorous exercise. There is a risk of physical injury during exercise, particularly if participants have little to no previous experience. Fatigue and muscle soreness may also occur in participants who do not normally engage in physical activity. Exercise is associated with a very small risk of serious medical complications including heart attack and sudden death, although this risk is particularly small in healthy older adults. Lastly, protocols currently exist to respond to any adverse events by contacting emergency response personnel and facilitating their arrival to the correct rooms (if the event occurs at the Center).

Participants will have contact information for study personnel should they have an unexpected adverse effect or question. The daily health messages contain information on how to contact study personnel if needed. Participants also receive a recruitment packet detailing contact information for study personnel to avoid technical failure (e.g., with accelerometers). We will send biannual safety reports to an independent safety officer, [name] [name], a neurologist and neuropsychologist who is not involved in the study. If an unexpected adverse event arises, the study team will alert the PI, [name] and [name] will inform [name] [name]. The PI will be made aware of any adverse outcomes. All research personnel will be trained in good clinical practice ethics modules.

#### Access to private health information

There is a potential risk of breach of confidentiality that is inherent in all research protocols. There is a possibility that if research data were to become generally known, this knowledge could potentially impact a subject's future insurability, employability, or reproduction plans, or have a negative impact on family relationships, and/or in paternity suits or stigmatization.

#### Exercise

There are several common risks associated with exercise participation including injury to muscles or joints, especially when initiating an exercise program after a period of being sedentary. Further, there is a minor risk of dehydration or heat exhaustion. More commonly, there is a risk of falling. Based on our considerable experience in walking and balance-based research assessments and interventions in adults, many of whom are much older than the cohort anticipated for enrollment into this study, we are confident that this risk is rare, meaning that it will occur in less than .001% (less than 1 out of 100000) of people in the otherwise healthy adults targeted for this study. This risk will be minimized as we are focusing on walking and reductions in sedentary behaviour rather than exercise training. Adverse or unstable cardiovascular or pulmonary response to exercise, including disorders of heart rhythm, heart attack, stroke, or sudden death will be minimized, because assessment of vital signs and history of heart disease are included in our screening procedures, and only those adults with satisfactory results as detailed in our eligibility criteria will be allowed to participate in experimental procedures for this study. As such, we anticipate that this risk is rare. According to American College of Sports Medicine (ACSM), guidelines published in 2000, the risk of myocardial infarction (MI) in symptomatic (categorized with males and females having ventricular arrhythmias) and asymptomatic (without any signs or symptoms indicative of ischemic heart disease) individuals during exercise is less than 0.04%. The risk of death in the same population is less than or equal to 0.01%, and the risk of needing hospitalization (including acute heart attack and/or serious arrhythmia) is less than or equal to 0.2%. The risk of cardiovascular complications occurring during exercise is rare (occurs in less than 1% of people). A retrospective survey by the YMCA revealed 1 death and 1 cardiac arrest per 2,897,057 and 2,253,267 person-hours. To minimize the risk, we are using a *non-exercise estimation of cardiorespiratory fitness* that requires BMI and heart rate measurement only.

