Physical activity will be measured with an ActiGraph accelerometer model GT9X Link (ActiGraph LLC, Pensacola, FL). The ActiGraph GT9X Link is a small (3.5 x 3.5 x 1 cm) and light (14 g) device that measures acceleration in three planes: vertical, anteroposterior and mediolateral. Participants will wear the device on their wrists 24 hours a day to improve compliance. The 24-hour protocol has resulted in greater compliance over waking time wear protocol [27]. Participants will be instructed to take the device off for swimming, showering and bathing. Data from this device will be synced with the CentrePoint app (HIPAA compliant, also through ActiGraph) on the participant's phone or computer. Raw data will be reduced and processed using ActiLife software (<http://www.actigraphcorp.com>). Participants will fill in sleep and activity logs.

The physical assessment administered at T1, T3, and T4 will involve the 2-minute walking test adapted from the NIH Motor Battery, a 20-second sitting-to-standing test (also used in the CDC's STEADI toolbox), and observations of balance while doing everyday activities like putting on shoes. We will record these physical assessments using Zoom. These are sensitive measures often used with older adults that reflect their fitness, especially their lower-body strength. Choosing these sensitive measures makes it more likely that we will be able to detect fitness changes post-test if the intervention results in the behaviour changes we expect.

[figure not shown]

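### The stated fall risk of under 1 in 100,000 has no given basis and sits in tension with its own section, and the documents describe no systematic ascertainment of falls

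*Protocol*

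**What the plan says.** Protocol section 9 (Risks), under Exercise, lists muscle and joint injury, then dehydration and heat exhaustion, and continues: "More commonly, there is a risk of falling". The ground offered for confidence is "Based on our considerable experience in walking and balance-based research assessments and interventions in adults", and the conclusion is that "this risk is rare, meaning that it will occur in less than .001% (less than 1 out of 100000) of people". No number of people observed, number of falls, observation period or reference is given.

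The same subsection cites a professional guideline for events during exercise: under 0.04% for myocardial infarction; for death, "The risk of death in the same population is less than or equal to 0.01" per cent; for hospitalisation, "including acute heart attack and/or serious arrhythmia) is less than or equal to 0.2" per cent. It then uses *rare* with a different limit: "The risk of cardiovascular complications occurring during exercise is rare (occurs in less than 1% of people".

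On capture, section 9 says: "Participants will have contact information for study personnel should they have an unexpected adverse effect or question". It adds that the daily health messages carry contact details, that biannual safety reports go to an independent safety officer, and that the PI learns of adverse outcomes. Section 5.5 has a video-recorded physical assessment at T1, T3 and T4 with a walking test, a sit-to-stand test and "observations of balance while doing everyday activities like putting on shoes". That observes balance during the session. It is not described as asking about falls between sessions.

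**The concern.** A numerical assurance in a risk section is read as evidence. This one is very strong, concerns adults over 60 who are encouraged to walk more, and has no data beside it. It is also lower than the ceilings the same subsection gives for death, infarction and hospitalisation during exercise, although falling is introduced as the more common risk.

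The second part matters more in practice. Falling is a listed risk, yet the described route for hearing about it is a participant deciding to contact staff about something *unexpected*. A fall without serious injury may not be seen that way.

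The route may also differ by arm. Contact details travel with the daily messages (sections 5.3 and 9), and the protocol is not consistent on what controls receive: Aim 1 in section 2 gives both arms health messaging, while section 4.1 describes the control as daily activity monitoring. If prompts differ, fall counts from passive reporting would not be comparable between arms. Section 11 plans to offer the intervention to a wider group of older adults if it succeeds, and a comparable count would be useful then.

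**Working it through.** **Inputs.** Fall ceiling 0.001%; death 0.01%; infarction 0.04%; hospitalisation 0.2%; second limit for *rare* 1% (all from Protocol section 9, Exercise). Sample size 120 (Protocol section 4.1) or 60 (SAP, Statistical Design and Power).

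1. **The plan's own figure.** 0.001/100 = 0.00001 = 1/100,000. The two forms agree. The figure cannot be derived, because no count, denominator or exposure period is given.

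2. **Experience needed to support it.** If no falls at all had been seen, the number of people needed for a 95% upper bound of p is n = ln(0.05)/ln(1 − p). With p = 0.00001, n ≈ 299,600. The rule of three gives 3/0.00001 = 300,000.

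3. **What it implies here.** Expected fallers are 120 × 0.00001 = 0.0012, or 60 × 0.00001 = 0.0006. The chance of at least one is 1 − (1 − 0.00001)^n, about 0.12% for 120 and 0.06% for 60.

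4. **Comparison within the subsection.**

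| Item | Stated ceiling | Ratio to fall ceiling |
|---|---|---|
| Death during exercise | 0.01% | 10 |
| Myocardial infarction | 0.04% | 40 |
| Hospitalisation | 0.2% | 200 |
| Second use of *rare* | 1% | 1000 |

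5. **What the trial could show.** With zero falls among n people, the 95% upper bound is 1 − 0.05^(1/n): 2.5% for n = 120 and 4.9% for n = 60.

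6. **Sensitivity (assumption).** The documents give no other fall rate. If between 0.1% and 10% of participants fell during the study, the expected number would be 0.12 to 12 of 120, or 0.06 to 6 of 60. That is 100 to 10,000 times the stated ceiling. The range is illustrative only.

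**The case against.** The strongest reply is that this is risk-disclosure wording with little statistical consequence. The figure enters no endpoint, sample size, eligibility rule or analysis. That stands, and it limits the weight of the point.

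Four stronger readings are tempting and should not be made.

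- *The section contradicts itself numerically.* The phrase introducing falls is relative to dehydration and heat exhaustion, which have no stated rate. The cardiovascular figures come from a guideline covering symptomatic and asymptomatic people during exercise, whereas the fall figure is the team's own, for healthy adults targeted by this study. The ratios therefore show tension, not strict contradiction. Likewise, anything under 0.001% is also under 1%, so the two uses of *rare* are loose but not incompatible.
- *The minimal-risk statement depends on the fall figure.* It does not. That statement in section 9 concerns serious adverse events of moderate-intensity exercise. The text beside it points to established procedures, the population and the focus on walking, and the Exercise subsection adds screening and eligibility. Removing the fall figure leaves it intact.
- *No session asks about falls.* This cannot be confirmed. Sections 5.5 and 6b refer to an attached spreadsheet of measures, and section 5.1 to a timeline document; neither is part of the public documents. Participants also complete activity logs whose content is not shown.
- *The trial will end with no fall count.* This is too absolute. A fall during a recorded assessment would be seen, staff contact participants who miss the daily survey (section 5.3), and the PI and safety officer receive adverse-event information.

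What remains is that the figure is unsupported, *rare* has two limits, and the documents describe no systematic ascertainment of falls.

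**Conclusion.** The point holds in a limited form. The bound of 1 in 100,000 has no count, denominator, time frame or source, and experience alone could support it only with about 299,600 fall-free people. It sits in tension with its own subsection, where *rare* also covers risks up to 1000 times larger.

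No inference about efficacy is affected. The practical consequence is that falls may be under-counted, and possibly unevenly by arm. The second part is conditional on the message-borne contact prompts differing between arms, which the documents leave unclear. The size of any under-count cannot be computed, because no credible fall rate is given. The ascertainment part assumes that the measures list, which is outside the public documents, contains no fall item.

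**What to change.** - Remove the .001% figure, or replace it with a sourced rate that states its denominator and time frame.
- Use one definition of *rare* throughout section 9.
- Unless the measures list already has such an item, add one fixed question on falls and injuries since the last session. Ask it in identical form in both arms at T2, T3, T4 and their period-2 equivalents. T3 falls at the start of week 4 (section 5.1), so confirm that T4 is timed to cover the final intervention week.
- Report the counts by arm, with the number of participants asked, in the biannual safety reports.

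The cost is a wording change and one item per existing remote session. The stated risk will look less favourable, and with 60 to 120 participants the counts will be imprecise. They would describe what happened in each arm, but could not establish that the risk is low.
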